To investigate the physiological mechanisms underlying fatigue, we will determine the associations among physiological measurements and PF, AF or MF. Firstly we hypothesize that the dynamics of AF will be associated with those of dynamic hyperinflation. By reducing dynamic hyperinflation using STIOLTO™ RESPIMAT® we hypothesize that dyspneogenesis will be reduced (e.g. reducing respiratory muscle work during exercise by reducing end-expiratory lung volume, and/or from reducing pulmonary mechanoreceptor activity during hyperinflation). We will measure dynamic hyperinflation with inspiratory capacity measurements during and following exercise and determine the association between dynamic hyperinflation and AF (secondary objective). Secondly, we hypothesize that MF at the limit of tolerance will be associated with increased muscle deoxygenation – the greater the MF the lower the muscle oxygenation consistent with a limitation to oxidative metabolism (secondary objective). These secondary objectives will be assessed using linear regression to determine the proportion of AF and MF that can be “explained” by e.g. dynamic hyperinflation, or leg muscle deoxygenation at isotime, end-exercise and during recovery.

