The purpose of the proposed study is to use a novel exercise testing protocol, designed and validated in our laboratories (Coelho et al., 2015), to determine the magnitude of PF, and its components (AF and MF) during and following whole body exercise in COPD. Bronchodilator treatment with the FDA-approved once-daily STIOLTOTTM RESPIMAT® (tiotropium bromide and olodaterol hydrochloride) versus placebo will provide an intervention designed to acutely improve pulmonary function in COPD and reduce dynamic hyperinflation in the absence of changes to peripheral muscle metabolism and fatigue processes contributing to MF. Combined measurements of dynamic hyperinflation and muscle oxygenation dynamics will allow us to relate changes in PF, AF and MF following STIOLTOTTM RESPIMAT® treatment to their putative physiological determinants. STIOLTOTTM RESPIMAT® is a combination long-acting anticholinergic and beta2-adrenergic agonist that produces greater increases in forced expiratory flow in 1 second (FEV1) compared the two drugs individually in GOLD stage 2-4 COPD patients (Ferguson et al., 2015).

This will be the first time that fatigue is measured *during* exercise in COPD with and without bronchodilator therapy. Previous studies have measured MF approximately 10 minutes after exercise cessation (Saey et al., 2003). However, preliminary data from our lab in COPD (unpublished; LA BioMed Protocol 30044-01) show that PF and MF are recovered by 90% or more after 2 minutes of recovery from exercise; meaning that the important exercise-limiting signals need to be measured *during* the exercise task itself. These preliminary data (n=13) show that MF is a minor contributor to exercise in COPD (20%), and the predominant cause of fatigue in COPD is AF (80%) (unlike in healthy young subjects). This suggestion supports the hypothesis that exercise limitation in COPD may be related to dynamic hyperinflation rather than to intramuscular limitations of muscle power production (MF).

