*Incremental exercise test:* All patients will perform a ramp-incremental cycle exercise on an electromagnetically-braked cycle ergometer (Excalibur Sport PFM, Lode NL) to the limit of tolerance after an overnight washout of short-acting bronchodilator (visit 2). Patients will breathe through a mouthpiece with nose clip in place for measurement of respired gases and volumes for breath-by-breath gas exchange and ventilatory measurements (Vmax Spectra, CareFusion USA). Tests will be administered with 3 minutes of rest and at least 3 minutes of unloaded cycling (until a steady-state is achieved), followed by an increase in power output at 5 W/min (for patients with  $FEV_1 \leq 1$  L) or 10 W/min (for patients with  $FEV_1 > 1$  L) and continued to the limit of tolerance. The limit of tolerance will be determined as the point at which the patient experiences intolerable dyspnea or is unable to maintain pedaling rate above 50 rpm despite verbal encouragement. At the limit of tolerance and every 1 minute during recovery an isokinetic power test will be performed (described below). At specified times during the exercise test, inspiratory capacity (IC) measurements will be made using a maximum inhalation. These will be made at rest, every 2 min during exercise, at end-exercise, and every 1 minute during recovery

*Constant work rate (CWR) exercise tests:* From an unloaded pedaling baseline (~3 min), the power output will be abruptly increased to approximately 75% WRpeak (this is the peak work rate achieved during the incremental exercise test). The specific work rate chosen will be chosen to elicit intolerance in ~6 min in the placebo condition (van der Vaart et al., 2013). The patient will be instructed and encouraged to maintain the power output for as long as they can manage (except in the isotime test, as noted below). Patients will breathe through a mouthpiece with nose clip in place for measurement of respired gases and volumes for breath-by-breath gas exchange and ventilatory measurements (Vmax Spectra, CareFusion USA). A familiarization CWR test will be performed at visit 2, at least 1 hour after the incremental test. At specified times during the exercise test, inspiratory capacity (IC) measurements will be made using a maximum inhalation. These will be made at rest, every 2 min during exercise, at end-exercise, and every 1 minute during recovery

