At baseline subjects will cycle at a comfortable cadence with zero load for ~3 min, after which they will be asked to perform 5 pedal strokes (~4 seconds) isokinetic cycling at each of ~25%, ~50%, ~75% and 100% maximal effort. The strain of the task is minimal and only a few seconds (~30 s) recovery is necessary between each effort, but subjects will be given as long as they feel is necessary to recover. During these efforts the flywheel braking of the cycle ergometer is controlled to result in predetermined velocities equating to a constant pedal cadence of 70 rpm. Patients will complete this test twice at baseline (unfatigued condition) prior to each exercise test to ensure reproducibility. If the two repeats do not cohere to within 10%, then the procedure is repeated a third time following a short (~10 min) rest. The patient will then be given 30 minutes to recover before the incremental or CWR exercise test is performed.

During each exercise test, isokinetic fatigue tests will be made at the point of limitation (or at isotime) and during recovery. For this the cycle ergometer will be switched to isokinetic mode and five pedal strokes will be completed at maximal effort (~4 seconds) to determine PF, AF and MF. In order to track fatigue during recovery, 5-pedal-stroke maximal isokinetic efforts will also be made every minute during recovery until the fatigue has recovered to 90% of the baseline value (up to a maximum of 6 minutes; 3-4 minutes is typical).

*Exercise NIRS:* Tissue oxygenation during exercise will be assessed by NIRS (as described above in *Non-invasive assessment of oxidative capacity by NIRS*). NIRS probes will be attached by adhesive tape to the skin of the quadriceps (for muscle oxygenation) and the forehead (for cerebral oxygenation), and a bandage will be placed over the probe to help ensure its stability during exercise.

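### The regression of activation fatigue on hyperinflation names no time or patient term; if recovery minutes are pooled, shared recovery alone can produce a non-zero proportion explained and excess false positives

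*Combined protocol and SAP*

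**What the plan says.** Protocol section 8 i, Analysis Plan, gives one method for the secondary objectives: "These secondary objectives will be assessed using linear regression to determine the proportion of AF and MF that can be" explained by, for example, "dynamic hyperinflation, or leg muscle deoxygenation at isotime, end-exercise and during recovery". No covariate, patient effect or time effect is named. Nothing says whether the listed time points are pooled or fitted one at a time.

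The AF hypothesis concerns time courses: "we hypothesize that the dynamics of AF will be associated with those of dynamic hyperinflation". The MF hypothesis is tied to one moment: "MF at the limit of tolerance will be associated with increased muscle deoxygenation".

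The data will be paired series. Under Procedures, inspiratory capacity (the hyperinflation measure) is taken "at rest, every 2 min during exercise, at end-exercise, and every 1 minute during recovery", and "5-pedal-stroke maximal isokinetic efforts will also be made every minute during recovery". The Measurements section places the capacity reading just before each AF and MF effort. Recovery efforts typically last 3 to 4 minutes, with a maximum of 6. Elsewhere in the Analysis Plan the rate of recovery is handled by repeated measures ANOVA, so time is a factor there but not in the regression.

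**The concern.** Once exercise stops, fatigue and hyperinflation both tend back towards rest whatever the causal relation between them. Regressing one on the other over those minutes picks up the shared clock. This is confounding by time. It is distinct from the repeated values within each patient, which make the p-value too small as a second and separate fault.

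A patient term alone does not cure the first fault. It removes the differences between patients that were diluting the shared trend, so the apparent share explained goes up.

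At stake is the mechanistic reading of the trial. A pooled R-squared could be reported as support for hyperinflation contributing to activation fatigue when the data would look the same with no link.

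**Working it through.** **The plan's own figure.** None is given for the regression. The only power figure, 0.95 for AF and MF, reproduces as a within-patient ANOVA: λ = f²·n·m/(1−r) = 0.23² × 21 × 3 / (1 − 0.80) = 16.66, power 0.950. This takes m = 3 measurements, a number the plan does not state. It does not cover the regression.

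**Inputs from the documents**
- 21 patients, two conditions to intolerance, end-exercise plus 3, 4 or 6 recovery minutes.
- Background, on the laboratory's own patients: "PF and MF are recovered by 90% or more after 2 minutes of recovery from exercise". If recovery is exponential, the half-time is at most 2 × ln 2 / ln 10 = 0.60 min.
- AF recovery is not stated directly. Background puts AF at 80% of fatigue and PF at no more than 10% of its end-exercise value by 2 min. With PF = AF + MF and MF not negative, residual AF is at most 0.10/0.80 = 12.5% of its starting value. That is three halvings in 2 min, or a half-time of at most 0.67 min.
- Against that, Background also cites a half-time of about 5 min for supraspinal fatigue in young subjects, longer in the elderly.

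**Inputs assumed, because the documents do not give them**
- Hyperinflation half-time 0.5, 1, 2 or 5 min.
- Between-patient coefficient of variation 0.3, 0.5 or 0.8, paired with measurement error of 0.10, 0.15 or 0.20 of the mean end-exercise value.

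**Simulation A.** Two conditions, 400 runs in each of 72 settings. AF and hyperinflation amplitudes are independent, so the true association is zero. AF half-time is 0.6 or 1 min. The regression has 21 × 2 × 4 = 168 to 21 × 2 × 7 = 294 rows.

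| Hyperinflation half-time | Mean pooled R², no time term | Runs with p<0.05 |
|---|---|---|
| 0.5–1 min | 0.12–0.69 | 89–100% |
| 2 min | 0.07–0.55 | 73–100% |
| 5 min | 0.025–0.28 | 36–100% |

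With minute as a factor, partial R² falls to 0.010–0.032. End-exercise only, in one condition, mean R² is 0.04–0.06 against a chance value of 1/(21 − 1) = 0.05, and p<0.05 occurs in about 5% of runs.

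**Simulation B.** One series per patient, end-exercise plus minutes 1–4, error 15%, log-SD of amplitudes 0.3 or 0.6, again with no link.
- Half-times from 0.5 to 5 min: pooled R² 0.04–0.61, p<0.05 in 33–100% of trials.
- Recovery minutes alone, without end-exercise: R² 0.03–0.23, p<0.05 in 20–99%. Fitting each phase separately but pooling minutes within recovery therefore does not avoid the problem.
- Patient-centred values (a patient term but no time term): R² rises from 0.16–0.60 to 0.38–0.68 with half-times of 0.5–2 min. It rises from 0.04–0.07 to 0.21–0.29 with both half-times at 5 min.
- Minute as a factor but no allowance for patient: R² is 0.02–0.04 with half-times of 0.5–2 min. Over half-times up to 5 min, p<0.05 still occurs in 11–36% of trials.
- Minute plus fixed patient intercepts, half-times 0.5–2 min: p<0.05 in 8–23%. An intercept does not absorb patient-specific decay.

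The MF–deoxygenation pair follows the same logic but was not simulated separately.

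**The case against.** The strongest reply is that the plan never says it will pool. A list of named time points fits a separate regression at each one equally well, and the MF hypothesis is set at a single point. On that reading, end-exercise and isotime show no artefact. This stands, and a reader who infers that the plan commits to a pooled fit goes further than the text. It is not a full answer. The AF hypothesis is about time courses, the secondary objective in section 4 covers the period during and after exercise, and recovery consists of several minutes with no rule for combining them.

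A reader might also infer that hyperinflation will appear to explain a large share of AF whatever the truth. The documents do not support that. They give no recovery rate for hyperinflation or deoxygenation. Fast AF recovery is an inference from the laboratory's data, and a slower central figure is also cited. When one half-time is 5 min and patient spread is wide, the spurious R-squared is only a few per cent, although the false-positive rate stays high.

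A third fair point is that adjusting for minute can discard real signal. When AF was made wholly proportional to hyperinflation, R-squared of 0.71–0.82 became a partial R-squared of 0.22–0.69. The adjusted figure is therefore conservative.

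Finally, section 4 words the objective as an association and makes no causal claim. That softens the consequence but does not make the p-value valid.

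**Conclusion.** The concern holds in conditional form. The plan leaves open a regression that, over end-exercise and recovery minutes, can return a non-zero proportion explained and a false-positive rate well above 5% with no link at all. Under assumed half-times of 0.5–5 min the pooled R-squared is about 0.04–0.6, with p<0.05 in 33–100% of trials. The upper part of that range needs fast recovery of both variables and moderate patient spread. These sizes rest on exponential recovery and on assumed spread, error and hyperinflation recovery. That the error rate is inflated held in every pooled setting tried; that the share is large did not. The AF–hyperinflation analysis is the exposed one. The MF hypothesis, kept at the limit of tolerance, is not affected. Neither a patient term alone nor a minute term alone is sufficient.

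**What to change.** In section 8 i, Analysis Plan, replace the sentence on linear regression with the following.

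1. The lead estimate of the proportion explained is the regression across patients at end-exercise, with one value per patient per condition. Fit the conditions separately, or together with a patient term.
2. Fit isotime separately. It comes from Visit 5 and from whichever condition gave the longer endurance, so it is not a point on the recovery clock.
3. Any analysis across end-exercise and recovery minutes includes minute as a categorical factor and accounts for repeated measures within patient. Either use a patient random intercept and slope over time, or take the p-value from a patient-level bootstrap or permutation. Permuting whole patient series keeps each patient's decay intact. Report the partial R-squared after minute.
4. An R-squared pooled over minutes without a time term is not presented as the proportion explained.

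The cost is a few sentences and a slightly larger model, with no new data, visits or patients. The reported proportion will be smaller. Because the minute factor also removes any true association carried by the common time course, describe the adjusted figure as a conservative estimate.

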**j) Confidentiality**

Data will be de-identified and stored on password-protected PCs and in locked cabinets. The PI and co-investigators will have access to the data. Data will be stored for at least three years, with the aim of indefinite storage. Data will be stored locally.

**k) Provisions to Monitor the Data to Ensure the Safety of Subjects\***

The data will be handled as source documents. These will include all data with patient demographics, history, questionnaires, pulmonary function, muscle

PROTOCOL TITLE: A randomized, crossover, placebo controlled, double-blind phase IV trial of the effect of on STIOLTOT™ RESPIMAT® on central and peripheral components of fatigue during exercise in chronic obstructive pulmonary disease  
Revised: November 13, 2015

oxidative capacity and exercise testing results. The documents will be filed in the subject's source document binder. This binder will also contain the properly executed consent form, the HIPAA (PHI) form as well as demographic data. The patient identifiers will be kept in this folder, but under a separate section from the study source data. This section will be marked as 'confidential' and the binders will be kept in a locked cabinet in a locked room. Access to the patient identifiers will be permitted only for the study coordinator and the person(s) with direct contact with the patient.

The PI will be responsible for reporting any adverse events to the local IRB utilizing the adverse event reporting policy established by the local IRB. All serious adverse events and non-serious adverse events which are relevant for a reported serious adverse event and Adverse Events of Special Interest (AESI) shall be reported to Boehringer Ingelheim Pharmaceuticals, Inc. Data monitoring will made on a per-procedure basis by the PI or co-investigators.

Per its policy, periodic data monitoring will be undertaken by a member of the Compliance Office at Los Angeles Biomedical Research Institute at Harbor-UCLA Medical Center.

**1) Withdrawal of Subjects\***

Participants will be free to withdraw at any time. Participants may choose to stop study treatment or leave the study at any time without it affecting their future care. Subjects are asked to discuss this decision with the study doctor. Subjects will be asked to return to the clinic for a follow-up visit and to return any unused study medication, but do not have to do this.

Participants are told that the study doctor may decide to withdraw them from this study at any time even without their consent. Participants will be withdrawn for any of the following reasons:

- Consent is withdrawn
- The subject is unwilling or unable to follow the rules of the protocol
- The subject becomes pregnant
- The subject experiences a medical emergency that makes it necessary to stop taking study treatment or that requires treatment assignment to be revealed to the study doctor and/or staff
- At the decision of the PI of one of the participating physicians

**9) Risks to Subjects\***

*Identification of risk and protections to minimize risk*

Our primary concern is the safety of the participant during exercise testing.

Participants will perform high-intensity exercise that may lead to physical discomforts (e.g. fatigue, delayed onset muscle soreness), but especially dyspnea in this patient population. The risks associated with participating in this study may

PROTOCOL TITLE: A randomized, crossover, placebo controlled, double-blind phase IV trial of the effect of on STIOLTO™ RESPIMAT® on central and peripheral components of fatigue during exercise in chronic obstructive pulmonary disease  
Revised: November 13, 2015

include, although unlikely, muscle cramps, muscle strain and/or joint injury, delayed muscle soreness, dyspnea, syncope, and fatigue. They may feel delayed muscle soreness (24-48 hr) after exercise. There is a risk of a cardiac event, such as a cardiac ischemia, cardiac arrest, dangerous arrhythmia, or acute cardiac collapse. This risk is approximately 1-2 occurrences in 10,000 tests of 'high risk' subjects with cardiovascular disease (American College of Sports Medicine). Similarly, an assessment of risk during high-intensity interval exercise testing and training of patients with coronary heart disease revealed approximately 1 event in over 23,000 hr of exercise, such as arrhythmia or myocardial infarction (Rognmo et al., 2012).

A person trained in CPR will be present during testing and a defibrillator is located within the laboratory in case of a cardiac event. A licensed physician will be available within the CDCRC for all study visits and will be in the room during each subject's initial incremental test. Participants will be coached to identify to the experimenters any unexpected symptoms and the exercise stopped immediately to mitigate risk during exercise testing. All tests are done with a 12-lead ECG and the test is stopped immediately should arrhythmic or ischemic patterns develop. **All tests are done with pulse oximetry and the exercise is stopped should oxygen saturation fall below 85%.**

All medications have the potential to cause side effects. The drugs involved in this study may involve risks that are already known, as well as risks that are currently unknown. Serious allergic reactions that can be life threatening may occur with any medication. However, we will take precautions to reduce these risks. Patients will be instructed to immediately report any allergic reactions to the PI, such as:

- a rash
- having a hard time breathing
- wheezing
- sudden dizziness, especially when standing
- swelling around the mouth, throat, or eyes
- fast pulse
- sweating

#### *Placebo Respimat®*

There are no known risks associated with using the placebo Respimat®.

#### *STIOLTO™ RESPIMAT®*

Combination treatment with tiotropium plus olodaterol (STIOLTO™ RESPIMAT®) has been studied in 6 completed clinical trials. The following side effects occurred in more than 3% of subjects:

- nasopharyngitis
- cough
- back pain

PROTOCOL TITLE: A randomized, crossover, placebo controlled, double-blind phase IV trial of the effect of on STIOLTOT™ RESPIMAT® on central and peripheral components of fatigue during exercise in chronic obstructive pulmonary disease  
Revised: November 13, 2015

Other side effects that occurred in less than 3% of patients are:

- dehydration
- dizziness, insomnia
- glaucoma, intraocular pressure increased, vision blurred
- atrial fibrillation, palpitations, supraventricular tachycardia, tachycardia, hypertension
- epistaxis, pharyngitis, dysphonia, bronchospasm, laryngitis, sinusitis
- dry mouth, constipation, oropharyngeal candidiasis, dysphagia, gastroesophageal reflux disease, gingivitis, glossitis, stomatitis, intestinal obstruction including ileus paralytic
- rash, pruritus, angioneurotic edema, urticaria, skin infection, and skin ulcer, dry skin, hypersensitivity (including immediate reactions)
- arthralgia, joint swelling
- urinary retention, dysuria, and urinary tract infection

*Use of short acting bronchodilators*

The study is a crossover design. Prior to beginning each new condition a 2 week washout from the study drug or placebo is required. This means that the COPD patients in the study will not be able to take long-acting anticholinergic or long-acting beta-agonist bronchodilators for several 2 week periods during the study. During this time they will be provided with a short-acting bronchodilator replacement medication (albuterol, or in some cases, Combivent) and be given instructions how to use it. In addition, any patients on combination therapies that include a long-acting bronchodilator will be required to discontinue its use prior to the study. This may include combination inhaled corticosteroid medications. These patients will be transitioned to a short-acting bronchodilator (albuterol, or in some cases, Combivent), and an inhaled corticosteroid monotherapy as appropriate.

*Albuterol*

Four puffs of albuterol will be given at visit 1 during the lung function tests, and will be provided as a short-acting bronchodilator medication. Albuterol is an FDA approved bronchodilator with mild side effects. Reported risks include:

- Very common (greater than 10%): Pharyngitis (sore throat).
- Common (3% - 7%): Headache, rapid heart rate, muscle and joint pain, dizziness, stuffy and runny nose, and unpleasant awareness of palpitations (strong heart beat).
- Uncommon (less than 3%): Chest pain, infection, diarrhea, inflammation of the tongue, accidental injury, anxiety, shortness of breath, ear disorder, ear pain and urinary tract infection.

*Combivent*

Combivent is an FDA approved short-acting bronchodilator containing albuterol and ipratropium bromide.

PROTOCOL TITLE: A randomized, crossover, placebo controlled, double-blind phase IV trial of the effect of on STIOLTOT™ RESPIMAT® on central and peripheral components of fatigue during exercise in chronic obstructive pulmonary disease

Revised: November 13, 2015

- Common side effects (greater than 2%) associated with Combivent include:  
Cough, shortness of breath, headache, bronchitis, sore throat, respiratory infection
- Uncommon side effects (less than 2%) include: High blood pressure, dizziness, tremor, muscle spasms or muscle pain, diarrhea, nausea, dry mouth, constipation, vomiting, weakness, flu-like illness, chest discomfort, eye pain, low blood potassium, palpitations (strong heat beat), fast heartbeat, skin itching or rash, pain in nose or throat, wheezing

Patients taking an inhaled corticosteroid in a combined therapy will transition to an FDA approved monotherapy at the beginning of the study. Risks of corticosteroids include:

- Common side effects (greater than 3%) associated with inhaled corticosteroids include: upper respiratory infections, throat irritation, upper respiratory inflammation, sinus infection, hoarseness, mouth or throat infection, cough, bronchitis, headache
- Uncommon side effects (less than 3%) include: runny nose or post-nasal drip, nasal sinus disorders, laryngitis, diarrhea, viral gastrointestinal infections, dyspeptic symptoms, gastrointestinal discomfort and pain, dry mouth, joint pain, muscle pain, muscle stiffness/tightness/rigidity, dizziness, migraines, fever, viral infections, pain, chest symptoms, viral skin infections, muscle injuries, soft tissue injuries, urinary infections

Pulmonary function tests represent minimal risk and are done routinely. In the past ten years there has been no adverse event precipitated by pulmonary function tests in our laboratory. Some people find the breathing tests tiring and occasionally patients experience a sense of dizziness, headache or shortness of breath that usually resolves quickly (common, mild seriousness). A few may experience a feeling of claustrophobia while in the body-plethysmograph. This usually passes as soon as the door is opened (uncommon, mild seriousness). The carbon monoxide content of the gas mixture used to measure lung diffusion capacity is low (0.3%) and the duplicate tests are done five minutes apart; therefore this test does not increase significantly carboxy-hemoglobin concentration.

Risks of adhesive tape allergy or discomfort from EMG and NIRS probes will be minimized using pinned-bandages in participants with adhesive allergies or those expressing adverse discomfort. The attachment and removal of the NIRS probe and EMG electrodes with adhesive may present a minimal, though brief, discomfort. Mild discomfort is common with the occlusion of extremity blood flow with the inflation of the blood pressure cuff during the resting NIRS measurement of oxidative capacity.

The risks associated with reading and filling out questionnaires are some psychological discomfort and anxiety.

PROTOCOL TITLE: A randomized, crossover, placebo controlled, double-blind phase IV trial of the effect of on STIOLTOT™ RESPIMAT® on central and peripheral components of fatigue during exercise in chronic obstructive pulmonary disease  
Revised: November 13, 2015

Only personal information essential to the research will be recorded, including age, anthropometric data such as height and weight, and physiologic data gathered during the experiments. These variables are important to define the patients enrolled for future publications. Personal health information is protected by conducting all data collection, storage, or transfer according to HIPAA Privacy regulations. Identifiable data will be securely stored and access is limited to the principal investigator and authorized assistants. Data will be coded as early in the research as possible and the code linking the data is stored in a locked cabinet. None of the data are considered to be sensitive or place the subject at legal risk. Personally identifiable data will not be disclosed to anyone other than the research team without the written consent of the subjects or their legal representative.

